3.2.3 Patient Characteristics

Patient disposition, including reasons for premature discontinuation of treatment or follow-up, number of patients in each analysis population (FAS, PPS, SS, PKS, ECHO Set, CM-ECHO Set), number and percent of randomized patients within each of the 3 randomization strata (previous treatment with Vyndaqel® or Diflunisal; disease stage; V30M TTR mutation) will be summarized by treatment group and overall for all randomized patients.

Patient allocation by investigative site will be tabulated by treatment group and overall for the all screened patients.

Protocol deviations will be listed and summarized by deviation category.

Patient demographic characteristics, including age, sex, race, ethnicity, TTR genotype, duration of disease from FAP diagnosis (months), and duration from onset of FAP symptoms (months) will be summarized by treatment group and overall for the SS, FAS, PPS, and CM-ECHO Set and for the PK and ECHO subgroups.

Baseline severity of illness, including the NIS score, mNIS+7, PND score, mBMI, BMI, weight, height, and NT-proBNP will be summarized by treatment group and overall for the SS, FAS, and PPS populations. Measures of quality of life and level of functioning, including the baseline Norfolk QOL-DN total score and pre-dose SF-36 will also be included. Information on familial amyloid cardiomyopathy (FAC) will be summarized, including FAC diagnosis (Y/N), duration of disease from FAC diagnosis (months), duration from onset of FAC symptoms (months), and clinical or laboratory criteria used to document the diagnosis of TTR cardiomyopathy.

Missing/partial dates (month and year) for the duration of disease from diagnosis for FAP/FAC and duration from onset of symptoms for FAP/FAC will be imputed as follows. Note that the day for these variables will not be imputed as this was not collected on the CRF. If year is missing no

imputation will be performed. If month is missing and the recorded year is before the year in informed consent date, the missing month will be imputed to be December, otherwise it will be imputed as the month from the informed consent date.

Exposure to Study Drug will be summarized for the SS by treatment duration (weeks), total volume (mL) and total dose administered (in milligrams, for the ISIS 420915 group only). The reason for dose pause will be tabulated. A listing summarizing for each subject the number of dose reductions (frequency of administered dose < protocol defined dose) and missed doses (injection not given) will be provided. Doses that were not given because the patient discontinued will not be summarized.

Medical history and baseline physical examination findings will be listed.

Medications will be coded using WHO Drug Dictionary. The final version used will be designated in the clinical study report. Prior medications, concomitant medications used while on-treatment and during the study will be summarized by treatment group for the SS and the CM-ECHO Set.

Prior and concomitant medications will be defined using the start and stop dates, and ongoing fields recorded in the CRFs relative to the first and last dose dates of randomised investigational product. A prior medication is defined as any medication taken up to, but not including the start date of investigational product. A concomitant medication is defined as any medication taken whilst investigational product is being taken. A concomitant medication is started during the post-treatment period (more than 7 days after last dose) will be considered an on-study medication but not on-treatment.

Note that if either of the start dates or stop dates of prior/concomitant medication are missing, the worst, or most conservative, case will be considered when slotting medications (i.e. the medications should slot into all possible phases). If a medication is administered pre-treatment or after first dose of investigation produce and no stop date/time is recorded then usage will be assumed to be ongoing for the remainder of the data collection periods. If a medication is stopped on-treatment or or after first dose and no start date/time is recorded it will be assumed that the medication was ongoing from prior to the start of investigational product. If a medication has no start or stop date it will be assumed that the medication was ongoing from prior to the start of investigational product.

If a partial date is recorded in the CRF, the following convention will be used to assign the medication:

- if the partial date is a start date, a '01' will be used for the day and 'Jan' will be used for the month
- if the partial date is a stop date, a '28/29/30/31' will be used for the day (dependent on the month and year) and 'Dec' will be used for the month.

The recorded partial date will be displayed in listings.

The definitions for prior, and on-treatment and on-study concomitant medication defined relative to use of the investigational product are shown schematically in the diagram below.

Scenario	Pre-treatment treatment	On-Study		PM	CM	
		On-treatment	Post-		On-trt	On-study
1	x-----x			Y	N	N
2	x-----x	-----x		Y	Y	Y
3	x-----x		-----x	Y	Y	Y
4		x-----x		N	Y	Y
5		x-----x	-----x	N	Y	Y
6			x-----x	N	N	Y
7	?-----x			Y	N	N
8		?-----x		Y	Y	Y
9		?-----x	-----x	Y	Y	Y
10	?-----?			Y	Y	Y
11	x-----?			Y	Y	Y
12		x-----?		N	Y	Y
13			x-----?	N	N	Y

PM = prior medication; CM – concomitant medication

x = start/stop date/time

? = missing date/time

3.3 Primary Analysis

3.3.1 Primary Endpoint Definition

There are two primary endpoints. The primary efficacy endpoints are the change from baseline to Week 66 in the mNIS+7 score and in the Norfolk QOL-DN questionnaire total score.

The mNIS+7 composite score has a maximum of 346.32 points. It can be broken into two components: the NIS component (maximum of 244 points) and the modified +7 component (maximum of 102.32 points). It can be further divided into the following 8 components: cranial nerves, muscle weakness, reflexes, sensory, heart rate deep breathing, nerve conduction, touch-pressure sensory, and heat-pain sensory.

The normal deviates (nds) from heart rate deep breathing and nerve conduction will be used in calculation of mNIS+7 for the primary analysis.

The mNIS+7 assessment is conducted at baseline (2 times), Week 35, Week 66 (2 times), and Week 91 (post-treatment). For visits where repeated assessments are done, the average will be used for analysis. Subcomponent scores will be averaged first, and the average composite score will be computed by summing the averaged subcomponent scores. Visits occurred after 52 days from the last dose of study medication are considered part of the post-treatment evaluation period, the data collected in the those visits will not be included in the efficacy analysis.

There are two scheduled visits for each of the two primary endpoints: Week 35 and Week 66. The data will be assigned to Week 35 or Week 66 according to the visit windows defined in section 3.2.1.3.

3.3.2 Primary Efficacy Analysis

The two primary endpoints, the mNIS+7 and the Norfolk QOL-DN questionnaire total score, will be tested using a ranking strategy with the mNIS+7 tested first and the Norfolk QOL-DN tested second. The primary efficacy analyses will be the contrast between the ISIS 420915 300 mg group and the placebo group at Week 66 from a Mixed Effects Model with Repeated Measures (MMRM) of change from baseline in each of these two endpoints during the treatment period. The primary analysis will be conducted using the Full Analysis Set (FAS). Interpretation will be made in a stepwise approach; should the null hypothesis, based on the mNIS+7, be rejected at a 2-sided 0.05 significance level, then the Norfolk QOL-DN questionnaire total score will be tested. However, if the null hypothesis for the mNIS+7 is not rejected, testing for the Norfolk QOL-DN questionnaire total score will be considered exploratory. No adjustment is therefore required for multiple hypothesis testing. This sequential testing procedure for the two primary objectives controls the overall Type I error rate at a 2-sided 0.05 level and is based on the methodology developed in Dmitrienko, Tamhane and Wiens (2008). The primary study hypotheses will be formally evaluated at the time of the end of treatment lock, occurring after all patients have completed the EOT assessments, the database is locked and treatment code is unblinded.

The MMRM method will include fixed categorical effects for treatment (two levels), time (two levels), treatment-by-time interaction, and each of the 3 randomization stratification factors (each with two levels). The baseline value of the endpoint and the baseline-by-time interaction will be included as fixed covariates in the model. Model parameters and treatment effects could be estimated by the following example SAS code:

CCI

In this model, missing data are not explicitly imputed (except for the assessment level data imputation specified in Section 3.2.1.3). Instead, all available post-baseline assessments of the endpoint during the treatment period (which fall in the Week 35 and Week 66 visit windows) for subjects in the FAS are utilized and via modelling of the within subject correlation structure, the endpoint treatment differences (which are adjusted to take account of missing data) are derived. The estimation of treatment differences is based upon the assumption that the missing data follows a missing at random mechanism (i.e. the missingness of the observations may be dependent on the observed outcomes or covariates, but not on unobserved outcomes).

The unstructured (2x2) covariance model will be used to model the within patient errors, shared across treatments and small sample adjustments to standard errors and tests will be made following

the Kenward-Roger approach (Kenward, M. G. and Roger, J. H. (1997)). In the unlikely circumstance that there are convergence problems with the repeated measures mixed model, this will be explored. For example the SCORING=4 option could be used in the PROC MIXED statement in SAS. This makes SAS use Fisher scoring for the first 4 iterations. If the convergence problem cannot be resolved the unstructured covariance matrix will be replaced by the restricted unstructured covariance matrix (Type=UNR in SAS). This also specifies an unstructured covariance matrix but with a different parameterization.

The treatment contrast for both Week 35 and Week 66 will be estimated by the model, with the Week 66 estimate considered primary. The normality assumptions for the MMRM models will be formally tested using a Shapiro-Wilks test at the 0.01 significance level and assessed by inspection of the following plots:

- Histogram of marginal studentized residuals derived from the MMRM model.
- Normal probability plot.

If the Shapiro-Wilks test assessing normality of the MMRM residuals from week 66 is statistically significant at the 0.01 level, formal hypothesis testing for that endpoint will be done at the 0.025 one-sided significance level using a non-parametric rerandomization test. Thus, the null hypothesis for the endpoint will only be tested using the results from the MMRM if the p-value from the Shapiro-Wilks test is > 0.01.

Steps for the rerandomization test are:

1. The MMRM detailed above will be fit using the randomized treatment and the estimated treatment effect (difference in least squares means between the treatment arms) at week 66 from this analysis will be stored and will be denoted by t^* .
2. Assignment to ISIS 420915 and Placebo is randomly shuffled within each of the eight study strata. Note that the shuffling will be done for all patients in the FAS irrespective of whether their post-baseline data falls within an analysis window. The MMRM is refit but now uses the shuffled treatment assignment (instead of the actual assigned treatment) and the estimated treatment effect at week 66 from the analysis is stored. This step will be repeated in the event that the MMRM does not converge.
3. Step 2 is repeated 50,000 times, where the collection of the estimated treatment effects under the shuffled treatment assignment defines the randomization distribution. Denote the treatment effect from the i th permutation of the data by t_i .
4. The p-value or the probability of observing a treatment effect as extreme as or more extreme than t^* under the null hypothesis of no treatment difference is estimated by

$$\frac{1 + \sum_{i=1}^{50,000} I(t_i \leq t^*)}{1 + 50,000},$$

where $I(A)$ is an indicator function that equals one if argument A is true, and 0 otherwise. If this one-side p-value is less than 0.025, the null hypothesis of no treatment difference will be rejected. The number of shuffled datasets may be increased depending if the simulation error in the estimated p-value is considered large.

If the rerandomization test is implemented, 95% CIs obtained by bootstrapping the data will be presented, with the resampling being done at the patient and not at the assessment level. A total of 10,000 bootstrap samples will be drawn, with the CI being defined as the 2.5th and 97.5th percentile from the empirical distribution of the treatment effect.

3.3.3 Additional Analyses of Primary Endpoints

In addition to the primary efficacy analysis, the following sensitivity analyses will be conducted on the FAS except where noted for each of the two primary efficacy endpoints:

- **Sensitivity Analysis 1 (Non-Parametric Analysis)** – The non-parametric Van-Elteren test will also be performed for the two primary study endpoints as the sensitivity analysis. Hodges-Lehmann estimates of the differences between ISIS 420915 300 mg group and the placebo group as well as distribution-free CIs based on the Wilcoxon Rank Sum Test will also be provided.
- **Sensitivity Analysis 2 (Conservative Assessment Level Imputation)** – To examine whether the primary analysis results are robust to the strategy for imputing missing assessment level data, an alternative strategy that results in a conservative estimate of the treatment effect will be implemented. Patients without an assessment at a visit will not have their score imputed for that visit. Imputation of missing baseline assessment level data will follow the approach detailed in Section 3.2.1.3. For patients with at least one non-missing post-baseline subcomponent score missing data will be imputed as follows. Missing post-baseline assessment level data will be imputed for the placebo group using their observed or imputed baseline value. Missing post-baseline assessment level data will be imputed for the ISIS 420915 group using the placebo mean in the Randomized population for that subcomponent at that visit (done after the placebo imputation).
- **Sensitivity Analysis 3 (Excluding Assessments done at Early Termination Visits)** – In order to examine the robustness of the primary analysis to the inclusion of premature termination data, the primary efficacy analysis will be repeated excluding data collected at early termination visits which are included in the primary analysis.
- Sensitivity analyses will be performed to investigate the impact of alternative missing data assumptions (see sections 3.3.3.2 and 3.3.3.3). These analyses will be done on the Safety Set and will be labeled as:
 - **Sensitivity Analysis 4** – Multiple Imputation assuming Missing at Random
 - **Sensitivity Analysis 5** – Multiple Imputation assuming Copy Increments from Reference
 - **Sensitivity Analysis 6** – Multiple Imputation assuming Jump to Reference
 - **Sensitivity Analysis 7** – Data at Withdrawal Visit Included
- **Sensitivity Analysis 8 (Per Protocol Set)** – The primary efficacy analysis will be repeated, using the PPS population.

- **Sensitivity Analysis 9** (Adjustment for Pooled Site) – The primary efficacy analysis will be repeated, but with the addition of pooled investigative site as a fixed categorical effect in the model. In the event that there are model convergence issues, results from this analysis will not be provided and will be noted in the study report. The interaction between treatment and pooled site will also be examined if model convergence permits.
- **Sensitivity Analysis 10** (Responder Analysis) – A responder analysis based on the change in mNIS +7 score will be conducted to examine whether improvement in response is consistent over a range of response thresholds. A responder is defined as a patient whose mNIS +7 score change from baseline to Week 66 is less than or equal to the threshold value. The relationship between response rate and thresholds will be summarized using a cumulative distribution plot. In addition, comparison of response rates for specific threshold values will be done. Thresholds that will be tested will include 0, 2, 4, 6, 8, 10, 15, 20, 30 points above the baseline value. For each of these specific response thresholds, the response rates at Week 66 for both the treated group and the placebo group will be calculated and plotted against the response threshold. Patients that terminate treatment early irrespective of the reason or had missing Week 66 data will be considered a non-responder. The difference in the estimated response rate and associated 95% CI based on the Mantel-Haenszel approach will be presented for each threshold.
- **Sensitivity Analysis 11** (HRDB and Nerve Conductions Scored Using Points and NIS-Sensation Excluded) – Additional sensitivity analysis on mNIS+7 composite score will be performed using the points (instead of Normal Dev) from heart rate deep breathing and nerve conduction and also removing the sensation part of the NIS.
- **Sensitivity Analysis 12** (HRDB Component Excluded) – Additional sensitivity analysis on mNIS+7 composite score will be performed, with HRDB not included as a component. HRDB will also be descriptively summarized for the group that has least one non-imputed HRDB score during efficacy treatment period and a non-imputed score at baseline.
- **Sensitivity Analysis 13** (Modified mNIS+7 Baseline Definition) – As outlined in Section 3.2.1.1, the primary efficacy analysis for mNIS+7 will be repeated using a modified baseline definition, defined as the average of two assessments taken within 60 days prior to the first dose of Study Drug.

Descriptive statistics will be provided for absolute values and change from baseline for Norfolk QOL-DN questionnaire total score by study visit. For mNIS+7 descriptive statistics by visit will be provided for absolute values, change from baseline and percent change percent from baseline. Data collected outside the analysis windows will be summarized.

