ISIS 420915-CS2 is a randomized, double-blind, placebo-controlled, multicenter study of approximately 15 months treatment duration and 6 months follow-up. Approximately 135 patients will be randomized in a 2:1 ratio (90 ISIS 420915 and 45 placebo) to receive 300 mg ISIS 420915 or placebo. Study Drug (ISIS 420915 or placebo) will be administered three times on alternate days during Week 1 (Days 1, 3 and 5), and then once weekly during Weeks 2–65 (for a total of 67 doses). The end-of-treatment (EOT) efficacy assessment is conducted at Week 66. Following treatment and the EOT efficacy assessment, eligible patients (including patients who received placebo) may elect to enroll in an open-label extension (OLE) study pending study approval by the IRB/IEC and the appropriate regulatory authority. All participating patients in the OLE study will receive 300 mg ISIS 420915 once weekly. Otherwise, patients will enter the 6 month post-treatment evaluation portion of the study.

Patients in the study will be Stage 1 (approximately 50%) and Stage 2 (approximately 50%) FAP patients with the following characteristics:

- a. Neuropathy impairment score (NIS) score ≥ 10 and ≤ 130
- b. Documented transthyretin variant by genotyping
- c. Documented amyloid deposition by biopsy

Interim safety data will be reviewed regularly by the ISIS 420915-CS2 DSMB.

A pharmacodynamic interim analysis of reduction in plasma TTR level will be performed by an independent statistician and reviewed by the DSMB after approximately 45 patients have completed the Week 13 visit. This interim will be a futility analysis and will result in a decision to continue the study as planned or to stop the study.

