2.2 Randomization & Treatment Allocation

Almac Clinical Technologies is responsible for providing the randomization for this study. Patients will be randomized after all screening assessments have been completed and after the Investigator has verified that they are eligible. No patient may begin treatment prior to randomization and assignment of a unique subject identification number.

Using an Interactive Voice-Response System (IVRS), eligible patients will be randomized 2:1 to receive ISIS 420915 or placebo, respectively. There will be 2 separate and independent randomizations, one for patients in the PK subgroup (approximately 20) and one for patients who are not in the PK subgroup (approximately 115). Within each subgroup, randomization will use a permuted block schedule using the 8 combinations of the following 3 binary stratification variables:

- Previous treatment with Vyndaqel® or Diflunisal versus no known previous treatment
- Stage 1 versus Stage 2 disease
- V30M TTR mutation versus non-V30M TTR mutation

A description of the randomization process, including block size and the procedure to follow will be provided in a separate document prepared by Almac Clinical Technologies.

The randomization list will be generated prior to enrollment of any patients. The Sponsor Quality Assurance department or designee will hold a copy of the randomization lists generated by the IVRS vendor.

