3.2.1 Analysis Conventions

All reporting will be performed in SAS version 9.1.3 or higher.

Efficacy results will be summarized under the treatment to which patients were randomized. Safety and PK results will be summarized under the treatment which patients actually received. Should there be any cases after unblinding in which a patient received treatment other than what was randomized, such cases will be discussed in the study report and noted in footnotes where applicable.

All electronic case report form (eCRF) data, lab data transfers, echocardiogram, ECG, and mNIS+7 score data, as well as any outcomes derived from the data, will be provided in the patient data listings. Patient data listings will be presented for all patients enrolled into the study, and will be sorted by treatment group, subject ID, visit, and time point (where appropriate).

Central laboratory assessments will be included in the summary tables, local laboratory assessments will only be included in listings. Exceptions to the use of local laboratory assessment in summary tables is made for platelets, where summary tables will use both local and central laboratory results

All tables will present the population frequencies in each treatment group and/or subgroup (where appropriate) and will indicate the number of subjects with non-missing data and the denominators for percentages.

Descriptive summary statistics including n, mean, percentiles (e.g., median, P25, P75), standard deviation, and range (minimum, maximum) for continuous variables, and counts and percentages for categorical variables, will be used to summarize data by treatment group. Summaries of pharmacokinetic parameters will also present geometric mean, standard deviation of log-transformed data, and CV%. Where appropriate, p-values will be reported. All statistical tests will be conducted using 2-sided tests with a 5% Type I error rate unless otherwise stated.

[figure not shown]
Age will be presented in years. Weight will be presented in kg. Height will be presented in cm. Temperature will be presented in °C. Laboratory values will be summarized using standard units.

Precision for displays will use the following conventions. Means, percentiles (e.g., median, P25, and P75), least squares means, difference in least squares means will be displayed to one more decimal place than measured values. Standard deviations and standard errors will be displayed to two more

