3.4.1 Secondary Efficacy Endpoint Definitions

Secondary efficacy endpoints are:

- Change from baseline to Week 66 in the Norfolk QOL-DN questionnaire symptoms domain score (Stage 1 patients only) and the Norfolk QOL-DN questionnaire physical functioning/large fiber neuropathy domain score (Stage 2 patients only)
- Change from baseline to Week 65 in the Modified Body Mass Index (mBMI)
- Change from baseline to Week 65 in the Body Mass Index (BMI)
- Change from baseline to Week 66 in the NIS
- Change from baseline to Week 66 in the modified +7

- Change from baseline to Week 66 in the NIS+7
- Change in GLS by ECHO from baseline to Week 65 in the Randomized Set, ECHO subgroup and in the CM-ECHO Set

Treatment group differences will be evaluated using the same method as the primary efficacy analysis (MMRM described in Section 3.3.2). These analyses will be conducted on both the FAS and the PPS populations. The analysis for GLS will be specified in the ECHO SAP.

The normality assumptions for the MMRM will be assessed for each of the secondary endpoints by inspecting the following plots:

- Histogram of marginal studentized residuals derived from the MMRM model.
- Normal probability plot.

The non-parametric Van-Elteren test may be performed as a sensitivity analysis, if deemed necessary. Hodges-Lehmann estimates of the differences between ISIS 420915 300 mg group and the placebo group as well as distribution-free confidence intervals based on the Wilcoxon Rank Sum Test will also be provided.

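### Sensitivity Analysis 1 pairs a stratified Van Elteren test with a Hodges-Lehmann interval that, on the ordinary reading, is unstratified, so the interval does not correspond to the test

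*SAP*

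**What the plan says.** SAP 3.3.3 states that "The non-parametric Van-Elteren test will also be performed for the two primary study endpoints as the sensitivity analysis". It then promises "Hodges-Lehmann estimates of the differences between ISIS 420915 300 mg group and the placebo group" and adds that "distribution-free CIs based on the Wilcoxon Rank Sum Test will also be provided". No strata are named for the test. Nothing says that the estimate or the interval is stratified or is derived from the Van Elteren statistic.

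SAP 3.4.1 repeats the pairing for the secondary endpoints, with "distribution-free confidence intervals based on the Wilcoxon Rank Sum Test". There the Van Elteren test is optional, while the estimates and intervals are worded as definite.

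Elsewhere the plan respects its strata. SAP 2.2 randomises "using the 8 combinations of the following 3 binary stratification variables". The primary MMRM in SAP 3.3.2 includes all three factors, and the fallback rerandomisation test in the same section shuffles treatment within the eight strata.

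**The concern.** Van Elteren compares active with placebo patients inside each stratum and combines the results. A Hodges-Lehmann interval from the two-sample Wilcoxon test uses every active–placebo pair, whichever strata the two patients come from. These are different statistics, so the p-value can fall below 0.05 while the interval includes zero, or the reverse.

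Readers will take the two together as one robustness result for each primary endpoint. If they conflict, the report has to explain a discrepancy that comes from the choice of method, and any interval substituted at that point would be post hoc. When the strata predict outcome, the unstratified interval also carries between-stratum variation that the test has removed.

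**Working it through.** **Inputs from the SAP.** About 135 patients, 2:1 (1.1). Eight strata from three binary factors (2.2). About half Stage 1 and half Stage 2 (1.1). Planned mNIS+7 effect 16 − 6.4 = 9.6 with SD 14; planned Norfolk QOL-DN effect 13.3 − 2.6 = 10.7 with SD 18; 25% dropout (section 4). On alpha, 3.2.1 says: "All statistical tests will be conducted using 2-sided tests with a 5% Type I error rate unless otherwise stated".

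**Assumptions not in the documents.** Normal outcomes; permuted blocks of 3; prevalences of the other two factors 0.5/0.5 or 0.6/0.35; additive stratum effects explaining a share R² of variance from 0 to 0.3; Van Elteren strata equal to the eight randomisation cells.

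**Step 1: reproduce the plan's power.** Evaluable patients are 135 × 0.75 ≈ 101, taken as 102 (68 active, 34 placebo). With √(68 × 34/102) = 4.761:
- mNIS+7: (9.6/14) × 4.761 − 1.96 = 1.305, power 0.904 (0.899 by noncentral t).
- Norfolk QOL-DN: (10.7/18) × 4.761 − 1.96 = 0.870, power 0.808 (0.800 by noncentral t).

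Both agree with the stated 90% and 80%.

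**Step 2: the two procedures.**
- Van Elteren: z = T/√V, with T = Σⱼ [Rⱼ − mⱼ(nⱼ+1)/2]/(nⱼ+1). Without ties, V = Σⱼ mⱼ(nⱼ−mⱼ)/[12(nⱼ+1)]. Here nⱼ is the stratum size, mⱼ the active patients in it and Rⱼ their rank sum within it.
- Unstratified interval: order all 68 × 34 = 2,312 pairwise differences. The limits are the C-th smallest and C-th largest, with C = ⌊2,312/2 − 1.96√(2,312 × 103/12)⌋ = ⌊1,156 − 276.1⌋ = 879.

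With eight equal cells (8.5 active, 4.25 placebo), only 8 × 8.5 × 4.25 = 289 of the 2,312 pairs, one in eight, lie within a stratum.

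**Step 3: how often they disagree.** There were 1,500 simulated trials per scenario. The table shows the 0.6/0.35 setting, as a percentage of trials (parts may not add exactly because of rounding).

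| R² | Endpoint | Only the test significant | Only the interval excludes 0 | Total |
|---|---|---|---|---|
| 0 | mNIS+7 | 1.3 | 3.5 | 4.9 |
| 0.1 | mNIS+7 | 2.3 | 1.7 | 3.9 |
| 0.2 | mNIS+7 | 3.1 | 1.0 | 4.1 |
| 0.3 | mNIS+7 | 3.5 | 0.6 | 4.1 |
| 0 | Norfolk | 2.1 | 4.9 | 7.1 |
| 0.1 | Norfolk | 4.1 | 3.5 | 7.7 |
| 0.2 | Norfolk | 5.5 | 1.8 | 7.3 |
| 0.3 | Norfolk | 7.6 | 0.9 | 8.5 |

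Over both prevalence settings the totals are 3.9–4.9% for mNIS+7 and 7.1–9.2% for Norfolk QOL-DN. Under the null they are 1.9–3.6%, and at half the mNIS+7 effect (4.8 points) 6.6–15.5%. A separate simulation with 135 randomised and 25% dropout (400 runs per scenario) gave 4–7% for mNIS+7. The unstratified Wilcoxon test agreed with the unstratified interval in at least 99.4% of runs, so the disagreement comes from the pairing.

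**Step 4: invert the Van Elteren statistic.** The interval is the set of shifts d for which |z| ≤ 1.96 after subtracting d from the active patients' outcomes. Under the Norfolk assumptions, with 400 trials each at R² = 0 and 0.2, disagreement was 0 of 400 both times. The unstratified interval disagreed in 5.3% and 8.3% of the same trials (standard error a little over 1 point). One trial gave Van Elteren p = 0.014, an unstratified interval of (−14.8, 1.2) and an inverted interval of (−16.7, −1.9).

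**Step 5: width.**
- Norfolk, R² = 0.2: mean 15.5 unstratified against 14.2 stratified.
- mNIS+7, R² = 0.3: 12.1 against 10.6 (ratio 1.14), with unstratified coverage about 98%.
- R² = 0: the stratified interval is the wider one, by about 2.5% (15.7 against 15.3, Norfolk) to 5% (mNIS+7).

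**The case against.** Much of the opposing case stands.

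- **Role.** This is one of 13 sensitivity analyses and it settles no hypothesis. Only the MMRM, or the rerandomisation test in its place, does that.
- **Other checks.** A reader might infer that this is the plan's only distribution-free check. It is not. SAP 3.3.2 has a rerandomisation test within strata, with bootstrap intervals, which becomes the formal test if the Week 66 residuals fail Shapiro-Wilk at 0.01. Sensitivity Analysis 10 adds a responder analysis for mNIS+7. What remains true is narrower: the rerandomisation test is conditional, so Sensitivity Analysis 1 is the only rank-based analysis of both primary endpoints that is always performed.
- **Borderline splits.** A reader might infer that a split makes the analysis uninterpretable. That is too strong. In a further simulation the larger of the two p-values in split trials had a median of about 0.07. Van Elteren against a plain t-test split about as often: 6–7% for mNIS+7 and 10–11% for Norfolk, against 6% and 9–10% for the pair at issue. The difference is that a test and its own interval are expected to agree, and two separate tests are not.
- **Power.** Stratification is not always better. With non-prognostic strata, Van Elteren power was 86% against 89% unstratified for mNIS+7, and 75% against 79% for Norfolk.
- **Validity.** The unstratified interval is valid: its null rejection rate was 4–5%. The SAP also never calls it unstratified; that follows from the test it names.
- **Sparse cells.** About 34 evaluable placebo patients over eight cells is 34/8 ≈ 4 per cell. In about 25% of simulated trials at least one stratum had one placebo patient or none. Any stratified method must say how it handles this.

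**Conclusion.** The point holds as a cheap improvement of low severity. The interval named in Sensitivity Analysis 1 is not the one that belongs to its test, and the Van Elteren strata are not stated. Disagreement on significance is about 4–7% at the planned mNIS+7 effect and about 7–9% at the planned Norfolk QOL-DN effect (9–10% in one further run). With prognostic strata the usual form is a significant test beside an interval that includes zero, and the interval is then wider than needed.

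These rates rest on the planning effects, SDs and dropout, and on assumed normality, block size, factor prevalences and an R² of 0 to 0.3. The documents give no value for R².

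A reader might go further and infer a threat to the primary conclusion or to type I error. The documents do not support that: SAP 3.3.2 places confirmatory testing elsewhere.

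**What to change.** Before unblinding, amend SAP 3.3.3 to say:
- the Van Elteren strata are the eight randomisation strata;
- a stratum with evaluable patients from only one arm contributes nothing to the statistic;
- the Hodges-Lehmann estimate and 95% interval come from inverting that same Van Elteren statistic.

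If the unstratified interval is still wanted, keep it as a supplement labelled unstratified and descriptive. Make the same edit in SAP 3.4.1, to apply wherever the Van Elteren test is run.

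The cost is a short text change and a small custom program, with no extra data. The downside is an interval roughly 5% wider if the strata turn out not to be prognostic.
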